5.4 Withdrawal Criteria

Patients can withdrawal from the study at any time. If the patient no longer wishes to participate, they will receive conventional care.

5.5 Conventional Therapy Criteria

The conventional therapy includes oral rinses and systemic therapy (oral, transdermal and intravenous analgesic. No response to conventional therapy means using other treatments and still symptomatic.

6.0 Methods

6.1 Patient enrollment and registration

Patients will be recruited for the study through multiple care sites at MD Anderson Cancer Center. Patients arriving at the MDACC Emergency Center with complaints consistent with mucositis will be screened for eligibility for enrollment in the study. Other patients treated at

the Pain Management Center as well as those referred for mucositis treatment from the Oncology medical wards for mucositis will also be screened.

6.2 Informed Consent

After patients are screened and found eligible for the study, they will be asked if they are interested in participating. If interested, patients will have the informed consent (IC) explained to them by a research team member. The study will use the electronic informed consent in EPIC to consent each participant, however, in the event that an electronic consent cannot be obtained, then the patient will sign, date, and put the time on the IC hard copy. The consenter will also sign, date and put time on the IC. A copy of the IC will be made and given to the patient for their records. The original copy will be sent to Health Information Management for storage and another copy will be locked in secure location by the principal investigator.

6.3 Patient randomization and assignment to treatment arm

The study will accrue up to 60 patients with a 1:1:1:1 ratio to include 4 intervention arms. Those include conventional therapy, conventional therapy + MB 0.025%, conventional therapy + MB 0.05%, and conventional therapy + MB 0.1%; each group will include 15 patients. We will conduct stratified randomization by baseline pain (baseline NRS 0-5 vs. 6-10) and oral functioning score (0-3 vs. 4-6). The primary endpoint is the reduction in pain score from baseline to 7 days. Patient randomization will be done through the Clinical Trial Conduct website. Study staff will be uninvolved in the randomization process.

Once a patient is enrolled in the study, the Investigational Pharmacy at MDACC retrieves the randomized treatment arm information from the Clinical Trial Conduct website. Once a patient is randomized to a treatment arm, Investigational Pharmacy will relay the information to the dispensing pharmacy at MDACC.

Study staff will contact patients either in person if as an inpatient or by phone at every follow-up the encounter to check for adverse events during routine patient encounters or via telephone calls.

Patients who were randomized to conventional arm will have an option to cross over to one of 3 MB arms, which they will be randomly allocated to, after completing 2 day pain measurements.

6.4 Administration of pharmacological agent

Preparation and randomization of the study medication (MB) for each patient will be performed by a compound research pharmacy. The study medication will be available to the patient through the dispensing pharmacy at MD Anderson Cancer Center. Patients will receive instructions on how to take study medications.

The participants will take MB via oral swish and spit technique or to continue conventional therapy. A small cup will be given to the patient to use to take the MB. There is no need for strict precision of the MB because patients' mouth size are variable, usually takes 6-10mL per rinse. Those on the MB arm will be instructed to take one mouth full (6 – 10 mL out of a total of 100 mL which might last 2-3 days only if used regularly) of the solution to be held at the painful sites for five minutes then to swish and spit. The same steps to be repeated every 6 hours (the total mix of 100 mL will provide up to 6-10 uses). If needed, patients will be given the solution to complete the treatment at home. Patients are instructed to use it every 6 hours until pain resolves or the total 100 mL of the mix are used. Therefore, the MB rinse is 3 total rinses per day, 6 hours apart.

Unused MB will be returned to Investigational Pharmacy Services at MDACC by the study staff for future incineration in accordance with the current SOP.

6.5 Data collection

Patients enrolled in the study will be asked to complete a baseline assessment questionnaire in person, including the Modified Harris mucositis-related pain assessment tool. The patient will have subsequent follow-up interviews at 1, 2, 7 days with repeat assessment of the Modified Harris mucositis-related pain assessment tool. Furthermore, on Baseline, Day 0, Day 1, Day 2, Day 7 and Day 30, adverse event will be assessed, and this maybe by telephone or face-to-face in the clinic. The patient's medication use will also be assessed at follow-up, including morphine equivalent daily dose (MEDD) and other reported analgesics used for the treatment of their mucositis-related pain. Lastly, the research team will investigate if any patient reported any side effects from the treatment.

All completed data will be stored electronically in the MD Anderson REDCap system, in a locked file, on password-protected computers. Only research team members will access the files. Subject registration will be entered into CORe database.

6.51 Modified Harris mucositis-related pain assessment tool (MHMPAT)

Among the numerous scales utilized for assessment of mucositis, most do not incorporate pain. The original Harris mucositis-related pain assessment tool was developed to fill the void of inadequate assessment of mucositis associated pain in existing assessment tools (18). The scale includes the NRS, which is one of the most widely utilized pain assessment measures in research and clinical care (17). Its use is related to its ease of administration. It uses an 11-point scale for measuring pain intensity (0 representing no pain, to 10 representing the worst possible pain). It is also beneficial for the current study, as it can accurately assess pain during telephone interview (17).

For this study we developed the Modified Harris mucositis-related pain assessment tool which has not yet been validated but incorporates aspects of many validated tools. It has been adapted with permission from the creator, [name], MSN, and OCN.

7.0 Data Analysis

Demographic information along with effectiveness data will be used to determine if there is a difference between the conventional care alone and the use of MB in addition to conventional care for the treatment of intractable pain associated with oral mucositis.

7.1 Sample Size Justification and Randomization

In a one-way ANOVA study, sample sizes of 15, 15, 15, and 15 are obtained from the 4 groups whose means are to be compared. The total sample of 60 subjects achieves 83% power to detect differences among the means versus the alternative of equal means using an F test with a 0.05 significance level. The size of the variation in the means is represented by their standard deviation which is 1.14 (means of 0, 2, 2.5, and 3 for conventional therapy, conventional therapy + MB 0.025, conventional therapy + MB 0.05, and conventional therapy + MB 0.1, respectively). The common standard deviation within a group is assumed to be 2.5. We will conduct stratified randomization by baseline pain (baseline NRS 0-5 vs. 6-10) and oral functioning score (0-3 vs. 4-6).

7.2 Primary Outcome Analysis

Descriptive statistics (means (SDs) or counts (percent)) will be used to summarize demographics, disease, and treatment variables according to the intervention arm. Potential differences between the arms based on demographic, disease, and treatment variables will be explored using Chi-square test or Fisher's exact test for categorical variables and ANOVA or Kruskal-Wallis test for continuous variables, depending upon the nature of the variables being investigated.

Our primary endpoint is the reduction in pain scores assessed within the NRS component of the Modified Harris mucositis-related pain assessment tool from baseline to 7 days which is considered the end of the study. The mean change in scores will be compared among 4 arms, utilizing ANOVA. If there are significant differences between intervention arms in some covariates, a linear regression model will be utilized to compare arms by adjusting for those significant covariates. The mean pain scores over time will be compared among study arms, utilizing linear mixed effects models. Covariates that showed significant differences among study arms will be adjusted in the linear mixed effects models. Two separate analyses, intention to treat and per protocol, will be conducted for primary analysis. Tukey's pairwise comparison will be conducted if a significant difference is observed among 4 arms. Intention to treat analysis population will include all patients who were randomized to one of treatment groups regardless of completion of the treatment. Per protocol analysis will include those patients who completed the treatment originally allocated. Patients who did not have 7day NRS will be replaced.

Patients who were initially enrolled in conventional arm and crossed over to one of MB arms will be included in assigned MB arm.

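### The primary ANOVA omits baseline NRS and the stratification factors unless they differ significantly between arms, which stratification all but rules out; this forgoes power and lets chance choose the model.

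*Combined protocol and SAP*

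**What the plan says.** The primary endpoint is defined in Section 6.3: "The primary endpoint is the reduction in pain score from baseline to 7 days". Section 7.2 gives the test: "The mean change in scores will be compared among 4 arms, utilizing ANOVA". Adjustment is conditional: "If there are significant differences between intervention arms in some covariates, a linear regression model will be utilized to compare arms", and that regression includes only the covariates found significant. The mixed models of pain over time follow the same rule: "Covariates that showed significant differences among study arms will be adjusted in the linear mixed effects models".

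The screen is described in the same section: "Potential differences between the arms based on demographic, disease, and treatment variables will be explored using Chi-square test or Fisher's exact test", with ANOVA or Kruskal-Wallis for continuous variables. The variables are not listed, no significance level is given for the screen, and neither baseline NRS nor oral functioning score is named in it.

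Section 7.1 (and 6.3) sets the allocation: "We will conduct stratified randomization by baseline pain (baseline NRS 0-5 vs. 6-10) and oral functioning score (0-3 vs. 4-6". Nowhere do the documents put either stratification factor, or baseline NRS as a continuous variable, into the primary model by default.

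**The concern.** The allocation and the analysis work against each other. Stratifying on baseline NRS and oral functioning forces the arms to be similar on both, so a test for imbalance will hardly ever be significant. The rule therefore leaves out the variables that were judged important enough to stratify on. Baseline NRS is one of the two terms in the change score, so the two are correlated unless something unusual holds.

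Two consequences follow. First, the variation between strata has been removed from the arm contrasts by the randomisation but remains in the ANOVA error term. The standard errors are then too large and the test is conservative. Second, whether any other covariate enters depends on a baseline significance test. In a randomised trial such a test detects only chance imbalance and says nothing about whether the variable predicts pain. The primary model is thus unknown until the data have been seen.

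**Working it through.** **1. The plan's own figure.** Inputs from Section 7.1: 15 patients per arm, mean reductions 0, 2, 2.5 and 3, within-group SD 2.5, alpha 0.05.

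- Grand mean = 7.5/4 = 1.875.
- Sum of squared deviations = 3.5156 + 0.0156 + 0.3906 + 1.2656 = 5.1875.
- SD of the means = √(5.1875/4) = 1.139, which matches the stated 1.14.
- Noncentrality λ = 15 × 5.1875 / 2.5² = 12.45, with 3 and 56 df.
- Power from the noncentral F = 82.7%. The stated 83% reproduces.

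**2. Power with baseline NRS in the model.** The documents give no correlation between baseline and day-7 NRS, so it is assumed and varied. Let both have variance σ² and correlation ρ.

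- Variance of the change = 2σ²(1 − ρ), held at 2.5².
- Residual variance after adjusting for baseline = σ²(1 − ρ²).
- Ratio = (1 + ρ)/2, so λ becomes 12.45 / [(1 + ρ)/2].

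With two covariates (3 and 54 df):

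| ρ | Variance ratio | λ | ANCOVA power |
|---|---|---|---|
| 0.3 | 0.65 | 19.15 | 95.7% |
| 0.5 | 0.75 | 16.60 | 92.5% |
| 0.7 | 0.85 | 14.65 | 88.7% |

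A third covariate (53 df) changes these by less than 0.1 point. If the covariates explained nothing, power with three of them would be 82.5%, a loss of about 0.2 point.

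**3. How often the rule would pick up baseline NRS.** This was simulated with 60 patients, four strata, permuted blocks of 4 and the screen at 5%; block size and screening level are assumptions. With strata of roughly equal size, baseline NRS was selected in 0 of 5,000 trials in every scenario. With unequal strata (up to a 90/10 pain split) it was selected in about 1% of trials at most. Without stratification the figure is about 5%, as expected.

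**4. Real type I error under stratification.** Simulated with blocks of 4 and a 50/50 pain split, nominal level 5%:

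| ρ | ANOVA | ANCOVA |
|---|---|---|
| 0.3 | 2.0% | 4.9% |
| 0.5 | 2.6% | 5.0% |
| 0.7 | 3.7% | 5.2% |

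An independent simulation at ρ = 0.5 gave 3.0% for ANOVA and 5.4% for ANCOVA, which agrees within simulation error. Simulated power at ρ = 0.5 was 83% for ANOVA and 92% to 93% for ANCOVA. Blocks of 8 give essentially the same picture.

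An uneven pain split brings ANOVA closer to nominal. At ρ = 0.5 its type I error is 3.5% for an 80/20 split and 4.0% for 90/10; at ρ = 0.7 it is 4.1% and 4.9%.

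**5. Chance entry of other covariates.** With k independent covariates screened at 5%, the probability that at least one is selected is 1 − 0.95^k: 23% for k = 5, 40% for k = 10 and 54% for k = 15.

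**The case against.** - **No shortfall against the plan.** The trial was powered for an unadjusted ANOVA and will use one. A change-score ANOVA in a randomised trial is unbiased and already uses each patient's baseline. This stands: what is lost is power that could have been had.
- **No false-positive risk.** In simulation the conditional rule had type I error of 4.3% to 4.8% without stratification and 1.1% to 3.9% with it. This also stands. The departure from the nominal level is conservative, and the 40% in step 5 is the chance that the model changes, not an error rate.
- **The size rests on assumptions.** Correlation, equal variances, block size, stratum split and number of covariates are not in the documents. Eligibility requires pain despite conventional therapy, so the low-pain stratum may be small and the conservatism mild. This is a fair reason to quote a range. At ρ = 0.8 and 0.9 the ANCOVA power would be about 87% and 85%. Those cases are less plausible, however: with a change SD of 2.5 they imply an NRS SD of 2.5/√0.4 = 3.95 and 2.5/√0.2 = 5.59, and an SD on a 0 to 10 scale cannot exceed 5.
- **Crossover and replacement are left out.** Section 7.2 counts controls who cross over in their MB arm, so the arms analysed are not quite the arms stratified. If half the controls crossed over, ANOVA type I error at ρ = 0.5 would be 3.4% (50/50 pain split) to 4.7%. Crossover and the replacement of patients without a day-7 NRS are separate and larger problems. They weaken the conservatism argument but give no reason to leave baseline NRS out.
- **The mixed models may use baseline.** They could, if day 0 is one of the modelled responses. The plan does not say so, and it applies the same screen to them.

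**Conclusion.** The concern holds. The rule in Section 7.2 excludes the stratification factors and baseline NRS in practically every trial and leaves the rest of the model to chance. For the same 60 patients, pre-specified adjustment would raise power from 83% to between 89% and 96%, a gain of about 6 to 13 points. That assumes equal variances at baseline and day 7, a change SD of 2.5 and a correlation of 0.7 to 0.3. The gain shrinks as the correlation rises, and the worst case is a loss of about 0.2 point. The unadjusted test is conservative, with a type I error of about 2% to just under 5% according to the correlation and the stratum split. The analysis is valid but inefficient and is not fully specified in advance. It should be changed, but it does not by itself undermine the trial.

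**What to change.** In Section 7.2, replace the conditional rule with one model fixed in advance: ANCOVA (or the mixed model, if that is made primary) with arm, baseline NRS as a continuous covariate, and oral functioning as a score or stratum. With baseline NRS in the model, analysing the change or the day-7 score gives the same arm contrasts. Delete selection by baseline significance tests from both the linear regression and the mixed models, and keep the baseline tables descriptive. If other covariates are thought prognostic, name them before any outcome data are seen.

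The cost is wording only. Both variables must be measured before randomisation because they define the strata, so no new data, visits or patients are needed. The model gives up 2 to 3 of 56 error degrees of freedom. The sample size need not change; the existing 83% can stay as the figure for an analysis without adjustment.

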4.0 Study Design

This study is a prospective, randomized trial involving adult patients with intractable pain associated with oral mucositis. This study will have four intervention arms - MB 0.025 arm, MB 0.05 arm, MB 0.1 arm and a control arm. MB arm will receive one of 0.025%, 0.05% or 0.1% MB solution in addition to conventional therapy (0.025%, 0.05%, and 0.1% MB solution for MB 0.025, MB 0.05, and MB 0.1 arm, respectively), and the control arm will receive conventional therapy for 2 days, then will receive one of 3 solutions which will be randomly selected if they would like to receive MB solution.

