5.0 Study Population

Patients will be randomized as described below. Neither the physician nor the patient will be involved in the randomization process. Physician, patient, study coordinator and data collectors will be blinded to the concentration of the medication used.

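### ITT and per-protocol are both called primary with no lead and no rule for conflict, and the per-protocol control group probably loses controls through an outcome-related exclusion

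*Combined protocol and SAP*

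**What the plan says.** Section 7.2 gives primary status to two analysis sets: "Two separate analyses, intention to treat and per protocol, will be conducted for primary analysis". It defines them as follows.

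- ITT: "Intention to treat analysis population will include all patients who were randomized to one of treatment groups regardless of completion of the treatment".
- Per-protocol: "Per protocol analysis will include those patients who completed the treatment originally allocated".

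The same section then adds, without naming the set to which it applies: "Patients who were initially enrolled in conventional arm and crossed over to one of MB arms will be included in assigned MB arm".

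Section 6.3 creates the crossover: "Patients who were randomized to conventional arm will have an option to cross over to one of 3 MB arms", and places it "after completing 2 day pain measurements", so before the Day 7 endpoint. Section 4.0 makes it the patient's choice; the control patient receives a solution "which will be randomly selected if they would like to receive MB solution". On masking, section 5.0 says: "Physician, patient, study coordinator and data collectors will be blinded to the concentration of the medication used". It does not say that MB versus control is masked.

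Sections 5.1 and 7.1 size the trial for one F test at one 0.05 level. No section says which analysis leads, whether one or both must be significant, or how the 0.05 is shared.

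**The concern.** Two primary analyses with no decision rule leave the trial's conclusion undefined when they disagree. If a significant result in either one is enough, the error rate of the primary conclusion is above the 0.05 on which the sample size rests.

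This is more than a labelling gap because the two sets differ in kind. A control who takes MB after Day 2 has, on the ordinary reading, not completed the allocated treatment, and so leaves the per-protocol set. The controls who remain are those who declined MB after a pain assessment. All patients entered with pain despite conventional therapy, so it is reasonable to expect that those who decline are more often those already improving. The plan does not say this and sets no pain threshold for crossover. This exclusion can occur in the control arm only, so randomisation no longer protects the comparison.

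**Working it through.** **1. The plan's own figure.** Inputs from sections 5.1 and 7.1: 15 per arm, mean reductions 0, 2, 2.5 and 3, within-group SD 2.5, alpha 0.05.

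- Grand mean = 7.5/4 = 1.875.
- Squared deviations: 3.5156 + 0.0156 + 0.3906 + 1.2656 = 5.1875.
- SD of means = √(5.1875/4) = 1.139 (plan: 1.14).
- Noncentrality = 15 × 5.1875 / 2.5² = 12.45, with 3 and 56 degrees of freedom.
- Power = 82.7% (plan: 83%). Reproduced.

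**2. Set-up of the error check.** Null trials were simulated: no MB effect, 15 per arm, SD 2.5, one-way ANOVA at 0.05 on ITT as randomised and again on per-protocol. Crossover fractions and the correlation between Day 2 and Day 7 change are assumptions; the documents give neither. If the two tests were independent, the chance that at least one is significant would be 1 − 0.95² = 9.75%. The sets overlap, so without selection the true figure is lower.

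**3. Exclusion unrelated to outcome.**

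- Only controls leave, 20% to 80% of them: either-test error 5.5% to 7.8%.
- Patients leave all arms at random, 90% down to 50% kept: 6.7% to about 8.5%.

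**4. Controls with least Day 2 improvement leave** (6,000 null trials per row; the last column is per-protocol mean reduction, MB minus control).

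| Crossover | Correlation | Per-protocol p<0.05 | Either p<0.05 | Per-protocol p<0.05 favouring MB | Bias, NRS points |
|---|---|---|---|---|---|
| 40% | 0.3 | 6.7% | 7.9% | 0.9% | −0.48 |
| 40% | 0.5 | 9.2% | 10.6% | 0.6% | −0.78 |
| 40% | 0.7 | 13.8% | 14.9% | 0.4% | −1.08 |
| 60% | 0.3 | 7.0% | 8.8% | 0.9% | −0.69 |
| 60% | 0.5 | 11.6% | 13.0% | 0.4% | −1.16 |
| 60% | 0.7 | 18.4% | 20.2% | 0.2% | −1.58 |

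Simulation error is about √(0.2 × 0.8/6,000) = 0.5 percentage points at the top of the range, and less below it.

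**5. Direction.** The bias is negative in every row: the controls who remain look better than MB. The F test has no direction, so these rejections count as significant. Counting only rejections in which pooled MB beats control (40,000 trials per scenario), either-test error is 2.5% to 2.7%, against 2.3% to 2.7% for ITT alone.

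**6. If both had to be significant.** The null error would be about 3% to 4%, so there would be no inflation. The plan does not say this.

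**7. If the crossover sentence also governs ITT.** With crossed-over controls counted in an MB arm, at 40% crossover and correlation 0.5, that analysis alone rejects under the null about 10.5% of the time.

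**8. Discordance under the planned means.** With correlation 0.5 and selective crossover, per-protocol power is 41% at 40% crossover and 23% at 60%, against 83% for ITT as randomised. The two analyses disagree in 42% and 59% of trials. These figures ignore dilution of ITT by controls who take MB, which would change them.

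**The case against.** Running ITT and per-protocol side by side is common, and both would presumably be reported. Four further points deserve an answer.

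- **Direction.** A reader might infer that the plan gives MB two chances of success and lets the sponsor pick the more favourable result. The calculations do not support that where the exclusion is selective. The second analysis then adds almost nothing to the chance of a false claim for MB; nearly all of the excess is control appearing better. This objection stands, and the 8% to 20% must not be read as false claims of benefit.
- **Conditionality.** Inflation needs a rule that either analysis suffices. The plan states neither that nor the reverse. This also stands; the defect is that the rule is missing.
- **Meaning of the allocated treatment.** Section 4.0 describes the control regimen as two days of conventional therapy followed by optional MB. A control who crosses over could then be said to have completed what was allocated and would stay in the per-protocol set. This reading is possible, so the exclusion is the ordinary reading and not a certainty. The plan needs to say which is meant.
- **Selection.** That decliners are those improving is inference. It is plausible, since the choice is voluntary, follows the Day 2 pain measurements, and is made without stated masking of MB versus control. The documents give no crossover rate or reasons.

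None of this supplies the missing lead analysis or decision rule.

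**Conclusion.** The concern holds in a limited form. It is certain that section 7.2 names two primary analyses without a lead or a rule for conflict. It is probable, on the ordinary reading, that one of them compares the MB arms with a control group selected after randomisation.

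The size depends on assumptions. If either analysis may carry the claim, the non-directional error is about 5.5% to 8.5% without selection and about 8% to 20% with it, and the selective bias runs against MB by about 0.5 to 1.6 NRS points. These figures assume that the worst Day 2 responders cross over, at 40% to 60%, with correlation 0.3 to 0.7. They also assume change measured from the original baseline; the plan does not define a baseline for patients who cross over, and a reset could alter the direction.

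A reader might also infer that ITT is a safe fallback as the plan stands. The documents do not establish that: the ITT definition does not say that patients are analysed in the arm assigned at randomisation, and the unrestricted crossover sentence may remove the same controls from the ITT control group.

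**What to change.** In section 7.2:

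1. Name one primary analysis: ITT, with all randomised patients analysed in the arm assigned at randomisation, at two-sided 0.05.
2. Make per-protocol a supportive analysis that cannot carry the primary claim, and state whether a control who took MB after Day 2 counts as having completed the allocated treatment.
3. Limit the sentence that places crossed-over controls in an MB arm to a named supportive analysis. Left unrestricted, it contradicts item 1.

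The cost is wording only, with no added patients: alpha stays at 0.05 and power at 82.7% under the planned means, before any dilution from controls who take MB. Keeping both analyses primary is dearer. Splitting alpha to 0.025 each lowers power to 74.0% at 15 per arm, and 18 per arm (4 × 18 = 72 patients) would be needed to reach 83.6%. It would also leave the selected control group inside the primary analysis.

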7.3 Secondary Outcomes Analysis

The mean change, from baseline to 7 days, in the Modified Harris mucositis-related pain assessment tool scores and the mean change in oral functioning scores will be compared between study arms, utilizing ANOVA or Kruskal-Wallis test (eat, swallow, talk: unable=2, difficulty=1, able=0. Oral functioning score is the total score of 3 categories, ranged 0-6). We will also determine if there are any differences between arms in presence or absence of pain, pain scores, overall analgesic use (including opiate use primarily used for oral mucositis pain via MEDD measurement), and the incidence of untoward side effects utilizing ANOVA, Kruskal-Wallist, Chi-square test, or Fisher's exact test as appropriate. In addition, to obtain a measure of compliance with MB treatment, we will compare the dropout rate within the MB group to the dropout rate in the conventional therapy group utilizing Chi-square test or Fisher's exact test.

The Investigator is responsible for completing an efficacy/safety summary report and submitting it to the IND office Medical Monitor for review. This should be submitted after the first 5 evaluable patients per arm, complete 7 days of study treatment, and every 5 evaluable patients per arm, thereafter.

In addition, the Patient Drug Administration log will be used to keep the record of drug usage. Duration of pain relief corresponding to each drug use will be collected during the interview, in person for Day 0 and via telephone for Day 1, Day 2, and Day 7. The number of MB doses needed (during the last 24 hours or since the last follow-up) in order to achieve pain relief will be collected on Day 1, Day 2, and Day 7.

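### The per-protocol set depends on completing treatment, which is undefined and tied to pain response, so one of two co-equal primary results is open to selection bias of unknown direction

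*Combined protocol and SAP*

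**What the plan says.** Section 7.2 plans two populations for the primary endpoint, the fall in NRS pain from baseline to Day 7: "Two separate analyses, intention to treat and per protocol, will be conducted for primary analysis". The ITT population is "all patients who were randomized to one of treatment groups regardless of completion of the treatment". For the other, "Per protocol analysis will include those patients who completed the treatment originally allocated". The plan does not say which of the two decides, and it does not say what completing treatment means.

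Three other places bear on that meaning:

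- **Section 6.4 (MB arms):** "Patients are instructed to use it every 6 hours until pain resolves or the total 100 mL of the mix are used". The same section says of the 100 mL supply that it is one "which might last 2-3 days only if used regularly".
- **Section 7.3 (efficacy/safety reports):** reports fall due after evaluable patients "complete 7 days of study treatment".
- **Sections 4.0 and 6.3 (control):** "the control arm will receive conventional therapy for 2 days", and "Patients who were randomized to conventional arm will have an option to cross over to one of 3 MB arms" once the Day 2 measurements are done. Section 7.2 then counts crossovers in the MB arm they move to, without saying whether this applies to the ITT set, the per-protocol set or both.

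**The concern.** Take two MB patients who each use three rinses and stop. One is pain-free and has followed Section 6.4 in full. The other is still in pain with solution left, and has not. Their exposure is the same, and only the pain result separates them. If completing means following the instruction, the second patient leaves the per-protocol set. If it means using the whole 100 mL, or seven days of treatment, the first patient leaves as well, and early responders are the people most exposed to exclusion. Either way, membership is decided partly by a close correlate of the primary endpoint.

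The control arm has its own outcome-related exit. A control patient who crosses over after Day 2 has, read literally, not completed the treatment first allocated, and patients still in pain have the most reason to cross over.

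The selection therefore works through different mechanisms in MB and control, and randomisation no longer protects the comparison. At stake is one of two analyses of equal standing. Someone who has seen the data could also choose the reading of completion that suits.

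**Working it through.** **Plan's own figure.** Inputs from Section 7.1: 15 per arm, mean reductions 0, 2, 2.5 and 3, within-group SD 2.5, alpha 0.05. The grand mean is 1.875 and the squared deviations sum to 5.1875. The SD of the means is √(5.1875/4) = 1.139 (stated 1.14). The noncentrality is 15 × 5.1875/2.5² = 12.45. With 3 and 56 degrees of freedom the power is 82.7% (stated 83%). The planning figure reproduces, so its SD is used below.

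**Do the notions of completion agree?** At 6 to 10 mL per rinse, 100 mL gives 100/10 = 10 to 100/6 = 16.7 rinses. Section 6.4 gives both a six-hourly interval and three rinses a day. At four a day the supply lasts 2.5 to 4.2 days, and at three a day 3.3 to 5.6 days. The section itself says 2 to 3 days. None of these reaches the seven days of treatment in Section 7.3.

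**Selection with no true effect.** Let the pain reduction X be N(0, 2.5) in every arm. Suppose each patient with X ≤ 0 leaves the per-protocol set with probability p. Half the arm has X ≤ 0, so a share p/2 is lost. The mean of those kept is

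p × 2.5 × φ(0) / (1 − p/2), with φ(0) = 0.3989.

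| Share of arm lost | p | Mean of those kept |
|---|---|---|
| 10% | 0.2 | 0.199/0.9 = 0.22 |
| 20% | 0.4 | 0.399/0.8 = 0.50 |
| 30% | 0.6 | 0.598/0.7 = 0.85 |

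The MB-minus-control difference is the MB entry minus the control entry. F-test rejection rates are from 15,000 simulated trials per setting, 15 randomised per arm. With no one lost the rate was 5.1%.

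| Loss in MB / control | Difference | F-test rejection |
|---|---|---|
| 10% / 0 | +0.22 | 5.5% |
| 20% / 0 | +0.50 | 7.3% |
| 30% / 0 | +0.85 | 13.3% |
| Equal loss (10%, 20% or 30%) | 0 | 5.0%, 5.0%, 4.7% |
| 10% / 30% | 0.22 − 0.85 = −0.63 | 7.8% |

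**If quick responders are excluded instead.** Suppose a share d of MB patients with X above 2.5 (one SD) is dropped and all controls are kept. The MB mean is −d × 2.5 × φ(1) / (1 − d × 0.1587), with φ(1) = 0.2420. For d = 0.5 this is −0.302/0.921 = −0.33. For d = 1 it is −0.605/0.841 = −0.72.

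**Sensitivity to the cut-off.** Defining a non-responder as a reduction below 1 point gives the same pattern. If 20% or 50% of MB non-responders are lost and no controls, the difference is +0.21 or +0.69. At equal loss it is about 0. At 20% of MB and 50% of control non-responders it is −0.47.

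The loss rates and cut-offs are assumptions, since the documents give none. They show sign and scale and are not forecasts.

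**The case against.** A reader might infer that the per-protocol analysis favours MB, because it keeps MB successes and sheds MB failures. The documents do not support that, for three reasons. First, Section 6.4 has a second route to the end of treatment: a non-responder who finishes the 100 mL has also completed and stays in, so only those who quit early in pain are lost. Second, counting quick responders as completers is only one reading, and the seven days in Section 7.3 points the other way. Third, control patients still in pain can leave the control set by crossing over. The positive differences above arise only because control loss is held at zero.

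The illustration is also severe in making every excluded patient a non-improver. People who stop because of taste, nausea or discharge would dilute the effect.

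It can also be said that the planned ITT analysis covers the problem. It does limit the consequence. It is not a full answer, because Section 7.2 does not make ITT decisive, and its rules on crossovers and on replacing patients without a Day 7 score weaken ITT too.

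A minimal-exposure definition can fairly be criticised as closer to a modified ITT set than to a per-protocol one. It would also keep controls who take MB between Day 2 and Day 7. Both criticisms stand and are carried into the fix as stated limits.

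**Conclusion.** The point holds as a defect of definition with bias of unknown direction. The absence of a definition of completion, the pain-dependent end of MB and the optional crossover are all in the text. Under the assumed loss rates the per-protocol difference with no true effect runs from about +0.9 through zero to about −0.7 points, against planned MB effects of 2 to 3 points. The F-test error rate reaches about 13% at worst in these settings. The sign depends on the reading of completion and on quitting and crossover rates that the documents do not give. Because per-protocol is one of two primary analyses with no ranking between them, this is worth correcting before data are seen. It does not show that the trial would produce a false positive for MB.

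**What to change.** In Section 7.2:

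1. Define the per-protocol set without reference to pain response or finishing the bottle: randomised, eligible, and at least one rinse of the allocated concentration (MB arms) or no MB through the Day 2 measurement (control).
2. State that the crossover sentence does not move control patients into MB arms in this set, and that their Day 7 value may reflect later MB use.
3. Name ITT by randomised arm as the decisive analysis, with per-protocol as supportive.
4. Report rinses taken by arm, using the drug administration log already planned in Section 7.3.

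Separately, Sections 6.4 and 7.3 must be reconciled on what completing treatment means. Which clinical rule applies is for the investigators.

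The cost is a short paragraph in Section 7.2 and one reconciliation, with no new data collection. The downside is that the per-protocol set will sit close to ITT and say less about full adherence. The descriptive rinse counts make up for only part of that.
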